9.4 End of 1st Treatment phase or Early Withdrawal (Week 6)

For participants who have completed the 6 week Phase 1 or have withdrawn early from the study, the following procedures will occur:

- Measure vitals (blood pressure, heart rate, respiratory rate, temperature), height and weight
- Physical exam performed by a study clinician or qualified staff member
- Collect stool sample (if possible) from subjects who have consented to stool collection
- Administer patient reported outcome questionnaires
- Assess AEs
- Obtain up to 4 biopsies from the esophagus for research purposes (taken during SOC EGD)
 - One of these esophageal biopsies will be used for EDP
- Research lab samples
 - Blood serum (~1-2 tsp, or 5-10 mL) for food IgE, CRD, and IgG4
 - Blood serum (~3-6 tsp, or 15-30 mL) for T cell studies
 - Blood (6-10 mL) or saliva (1-2 mL) for future genetic testing may be collected at this visit (if not collected previously)
 - Blood for metabolomics (1 tsp, or 3-5 mL)
 - CBC with differential - if a CBC with differential was obtained clinically as part of standard of

care, obtain the results from the standard of care CBC

- Assess participant compliance with diet therapy and concomitant medications
- Pregnancy Test (urine)

Stool samples may be collected from participants who have consented to stool collection. Stool will only be collected at some, but not all, participating centers.

If a participant withdraws from the study before completing 6 weeks of dietary therapy, the end of treatment/early withdrawal visit should be conducted within one week of the participant's stopping dietary therapy. Participants should stay on their dietary therapy until results of biopsies are communicated to them.

Those participants who have resolution of their inflammation on endoscopy at the end of Phase 1 will complete the study at this time. Subjects with continued active inflammation will move on to phase 2, 6FED non-responders will start treatment with swallowed SGC (880mcg BID fluticasone propionate) and unrestricted diet and 1FED non-responders will start treatment of 6FED.

9.5 Phase 2 Visit 1 (Week 10)

Those participants who have completed the phase 1 diet protocol but have continued active inflammation may choose to continue into Phase 2 and will return to clinic once their biopsies have been read. This visit should happen within 4 weeks of their EGD. At this visit, the following procedures will occur:

- Measure vitals (blood pressure, heart rate, respiratory rate, temperature), height and weight
- Assess AEs
- Assess participant compliance with concomitant medications
- Provide standardized instructions for administration of the fluticasone (for participants who will be on fluticasone)
- Provide standardized instructions for 6FED for participants who will be on 6FED
- Provide diet or medication diary/log to participants
- Administer dietary questionnaire to measure *intake* of the 6FED food allergens (for those who will be on 6FED)
- Complete DSQ
- Dispense fluticasone to participant (for those moving on to SGC)
- Measure morning cortisol (serum, ~1 tsp or 5 mL) (for those moving on to SGC in Phase 2)

9.6 Phone Visits, Phase 2

A study staff member will conduct two phone visits (at weeks 11 and 15) during Phase 2 in order to monitor participants' progress throughout the trial. The following procedures will occur during these phone visits:

- Assess con-med and/or con-therapy compliance
- Assess AEs
- Determine compliance with dietary treatment

- A dietary questionnaire to measure *intake* of the food allergens will be completed by participants who are on 6FED during weeks 11 and 15
- A food diary will be completed by participants who are on 6FED during weeks 11 and 15 to measure adherence
- Daily completion of the DSQ within the two weeks prior to the Phase 2 EOT EGD (Weeks 14 and 15)

9.7 End of 2nd treatment phase or Early Withdrawal (Week 16)

For those participants who have completed the phase 2 therapy or have withdrawn early from the study, the following procedures will occur:

- Measure vitals (blood pressure, heart rate, respiratory rate, temperature), height and weight
- Physical exam performed by a study clinician or qualified staff member
- Administer patient-reported outcome questionnaires
- Assess AEs
- Obtain up to 4 biopsies from the esophagus for research purposes (taken during SOC EGD)
 - One of these esophageal biopsies will be used for EDP
- Assess participant compliance with therapy (SGC) and concomitant medications
- Pregnancy Test (urine)
- Measure morning cortisol (serum, ~1 tsp, or 5 mL)
- Collect fluticasone from participant (for those on SGC)
- Collect participant compliance logs; dietary log or SGC log
- Research lab samples
 - Blood (6-10 mL) or saliva (1-2 mL) for future genetic testing may be collected at this visit (if not collected previously)
 - Obtain CBC with differential (2-3 mL)- IF a CBC with differential was obtained clinically as part of standard of care within the screening period, obtain the results from the standard of care CBC

If a participant withdraws from the study before completing 6 weeks of SGC or 6FED therapy in Phase 2, the end of treatment/early withdrawal visit should be conducted within one week of the participant's stopping therapy. Participants should stay on SGC or 6FED until results of biopsies are communicated to them. Following the receipt of their biopsy results, the participant will return to standard clinical care.

Should pregnancy occur during either phase of the study, dietary therapy and/or dosing of study medication will be discontinued and the participant will be withdrawn from the study. The pregnancy will be followed clinically to term.

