1. INTRODUCTION

The primary objective of this proposal is to conduct a prospective, non-blinded randomized trial comparing rates of remission of novel empiric elimination dietary therapies in eosinophilic esophagitis (EoE) in order to assess the therapeutic viability of empiric elimination diets. Moreover, we aim to assess response to topical swallowed steroids in non-responders to empiric six food dietary therapy regimens and the response to 6FED in 1FED non-responders. Participants aged 18 to 60 years with active EoE will be enrolled and the primary efficacy outcome will be the rate of histologic remission assessed using esophageal biopsies obtained following a six week randomized trial of one of two empiric diets. During the screening process, active EoE will be confirmed by histologic evaluation of esophageal biopsies obtained during an esophagogastroduodenoscopy (EGD) in subjects with a history consistent with EoE.

This trial is comprised of a screening (up to 12 weeks in duration) and 2 phases, with each phase lasting 6 weeks. Phase 2 is optional, and eligible participants may choose whether or not to continue into Phase 2. In the first phase, all participants will be randomized 1:1 to either 1 food elimination (milk elimination alone, 1FED) or 6 food elimination (milk, egg, wheat, soy, fish/shellfish, peanut/tree nuts elimination, 6FED) therapeutic diet. At the end of this phase, an EGD will be performed to assess remission. Attainment of remission (esophageal eosinophil counts <15 eosinophils/high powered field) after phase 1 will result in study discontinuation and maintenance of the “successful” dietary therapy. Dietary therapy non-responders who were on 6FED during Phase 1 and choose to continue into Phase 2 will receive topical swallowed steroids for 6 weeks (Phase 2) while on an unrestricted diet, followed by EGD with esophageal biopsies. Dietary therapy non-responders who were on 1FED during Phase 1 and choose to continue into Phase 2 will proceed to 6FED for six weeks (Phase 2) followed by EGD with esophageal biopsies.

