9. STUDY PROCEDURES

9.1 Screening/Baseline Visit (Weeks -12 to -1)

The screening visit should occur at a maximum of twelve weeks and a minimum of 1 week prior to the enrollment visit. A research staff member will perform the informed consent process. After obtaining informed consent, the following study procedures will be performed and documented:

- Assess eligibility (inclusion and exclusion criteria)
- Collect Medical, surgical and diet history
- Vitals (height, weight, blood pressure, heart rate, respiratory rate, temperature)
- Demographics (age, gender, race)
- Physical exam performed by a study clinician or qualified staff member
- Collect stool sample (if possible) from subjects who have consented to stool collection

- Obtain up to 4 biopsies from the distal and proximal esophagus for research purposes (taken during standard of care EGD)
 - One of these esophageal biopsies will be used for EDP
- Research lab samples
 - Blood (6-10 mL) or saliva (1-2 mL for future genetic testing may be collected at this visit)
 - Blood for metabolomics (3-5 mL)
 - CBC with differential (2-3 mL)- if a CBC with differential was obtained clinically as part of standard of care within the screening period, obtain the results from the standard of care CBC
- Assessment of concomitant medications and therapies
- Pregnancy Test (urine)

Participants may qualify for rescreening if they are ineligible due to any of the reversible illnesses listed in the exclusion criteria if their condition improves while recruitment is ongoing and they still fall within the screening window.

Esophageal biopsies for research may be taken during a participant's standard of care EGD (SOC EGD). If the participant has had an EGD and biopsies performed prior to the screening visit, the results of the EGD may be used to determine eligibility if it falls within the four-week window prior to enrollment. EGDs performed at an outside institution may be used as baseline if the corresponding pathology report and slides are available and the eosinophil counts meet the inclusion criterion of ≥ 15 eosinophils/hpf. In cases where the local pathologist has concerns regarding the eosinophil count, slides may be sent to the CRPC for rapid review in order to verify eligibility.

The amount of blood drawn (clinical plus research) will follow the NIH clinical center guidelines "Guidelines for Limits of Blood Drawn for Research Purposes in the Clinical Center" (May 26 2012).

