9.2 Enrollment (Week 0)

All eligible participants will be enrolled into the study at Week 0 if they meet all entry criteria and have completed the screening procedures. Study procedures will not be repeated if the enrollment visit takes place within 5-10 business days of the screening visit. At this visit, staff members will:

- Assess eligibility (inclusion and exclusion criteria)
- Measure vitals (blood pressure, heart rate, respiratory rate, temperature), height and weight
- Obtain stool sample (if possible and not collected at Screening/Baseline) from subjects who have consented to stool collection
- Administer patient reported outcome questionnaires, which will include dietary questionnaires to measure *intake* of the food allergens and a food diary to assess baseline diet
- Completion of DSQ
- Assess concomitant medications and/or therapies

- Skin testing for allergies including prick and patch testing
- Randomize eligible participants to the 1FED or 6FED diet
- Provide standardized dietary instructions for 1FED or 6FED
- Research lab samples
 - Blood serum (~1-2 tsp, or 5-10 mL) for food IgE, CRD, and IgG4
 - Blood serum (~3-6 tsp, or 15-30 mL) for T cell studies

The participants will be encouraged to call the PI and/or study coordinator if they have any questions, concerns, adverse events, or changes in medication.

Stool samples may be collected from participants who have consented to stool collection at the Enrollment visit if they were unable to be obtained at the Screening/Baseline visit. Stool will only be collected at some, but not all, participating centers.

9.3 Phone Visits, Phase 1

A study staff member will conduct three phone visits (at weeks 1, 3, and 5) during Phase 1 in order to monitor participants' progress throughout the trial. The following procedures will occur during these phone visits:

- Assess con-med and/or con-therapy compliance
- Assess AEs
- Determine compliance with treatment
 - A dietary questionnaire to measure *intake* of the food allergens will be completed by the participants during weeks 1 and 5
 - A food diary will be completed by participants during weeks 1 and 5 to measure adherence
- Daily completion of the DSQ within the two weeks prior to the Phase 1 EOT EGD (Weeks 4 and 5)

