12.3 Grading and Attribution of Adverse Events

12.3.1 Grading Criteria

The study site will grade the severity of adverse events experienced by the study subjects according to the criteria set forth in the National Cancer Institute’s Common Terminology Criteria for Adverse Events (CTCAE) [*Version 4.03, June 14, 2010*] This document (referred to herein as the NCI-CTCAE manual) provides a common language to describe levels of severity, to analyze and interpret data, and to articulate the clinical significance of all adverse events. The NCI-CTCAE has been reviewed by the Protocol Chair and has been deemed appropriate for the subject population to be studied in this protocol.

Adverse events will be graded on a scale from 1 to 5 according to the following standards in the NCI-CTCAE manual:

Grade 1 = mild adverse event.

Grade 2 = moderate adverse event.

Grade 3 = severe and undesirable adverse event.

Grade 4 = life-threatening or disabling adverse event.

Grade 5 = death.

For grading an abnormal value or result of a clinical or laboratory evaluation (including, but not limited to, a radiograph, an ultrasound, an electrocardiogram etc.), a treatment-emergent adverse event is defined as an increase in grade from baseline or from the last post-baseline value that doesn’t meet grading criteria. Changes in grade from screening to baseline will also be recorded as adverse events, but are not treatment-emergent. If a specific event or result from a given clinical or laboratory evaluation is not included in the NCI-CTCAE manual, then an abnormal result would be considered an adverse event if changes in therapy or monitoring are implemented as a result of the event/result.

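### Protocol 9.7 repeats the screening-visit CBC clause at Week 16, so read literally a pre-treatment blood count can supply the end-of-Phase-2 value, in conflict with the Schedule of Assessments

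*Protocol*

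**What the plan says.** Protocol section 9.7 lists the procedures for Week 16 or early withdrawal from Phase 2. Its CBC item starts with an instruction to obtain the count (2-3 mL) and continues: "IF a CBC with differential was obtained clinically as part of standard of care within the screening period, obtain the results from the standard" (that is, from the clinical count). Section 9.1, for the screening visit, carries the same condition.

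Section 9.4, for Week 6, has a related provision that begins "if a CBC with differential was obtained clinically as part of standard of" (again meaning routine clinical practice). It does not mention the screening period and states no time window of its own.

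On timing, section 9.1 says: "The screening visit should occur at a maximum of twelve weeks and a minimum of 1 week prior to the enrollment visit". Randomization and diet instruction take place at Week 0 (section 9.2), and Phase 2 opens at Week 10 (section 9.5). The Schedule of Assessments marks a CBC at Visits 1, 6 and 10 and attaches no footnote to that row. Section 9.9 allows plus or minus 3 days for Visits 2 to 10.

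For abnormal laboratory results, section 12.3.1 says "a treatment-emergent adverse event is defined as an increase in grade from baseline or from the last post-baseline value". The rest of that sentence limits the post-baseline comparator to a value that does not reach a grade.

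**The concern.** A rule that accepts a recent clinical CBC in place of a research draw is sensible at screening, where the screening period is the time of interest. At Week 16 the same words refer to a period that closed before randomization. Read the way it works in 9.1, the clause lets a pre-treatment count fill the Week 16 field, and that count carries no information about Phase 2.

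What is at stake is laboratory safety data. Section 12.4.1 says an abnormal laboratory result can indicate an adverse event, and section 12.3.1 decides whether it is treatment-emergent by comparing grades. Adverse events from both phases go into the SAP's summaries and Fisher's exact comparisons. A screening value entered as the Week 16 result can therefore put a wrong entry, or no entry, into those tables.

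**Working it through.** **Age of the value.** The documents state no figure for this, so it follows from the visit calendar.

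- Inputs: screening runs from Week -12 to Week -1 (9.1), the end of Phase 2 is Week 16 (9.7), and Phase 2 starts at Week 10 (9.5).
- Formula: age = visit week minus CBC week.
- Oldest at Week 16: 16 - (-12) = 28 weeks. With the +3-day window, 28 weeks 3 days.
- Youngest at Week 16: 16 - (-1) = 17 weeks. With the -3-day window, 16 weeks 4 days.
- Age already reached when Phase 2 opens: 10 - (-12) = 22 weeks at most, 10 - (-1) = 11 weeks at least.

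Every value the clause admits predates Week 0, and so predates both diets and the swallowed steroid. Early withdrawal from Phase 2 gives a shorter interval, but the value is still pre-treatment. The synopsis gives a maximum study duration of 27 weeks, whereas Week -12 to Week 16 spans 28. That one-week mismatch does not change the conclusion.

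**The CBC provisions side by side.**

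| Place | Clinical CBC accepted from | Fits the visit? |
|---|---|---|
| 9.1, screening | screening period | yes |
| 9.4, Week 6 | no period stated | yes, if read with the Week 6 visit window |
| 9.7, Week 16 | screening period | no |
| Schedule, Visits 1, 6, 10 | separate CBC at each, no exception | conflicts with 9.7 |

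**Effect on the adverse event rule.** The Schedule has no CBC at Visit 2, so I take the screening count as baseline. Write 0 for a value that does not reach a grade. If the screening value is reused, the recorded Week 16 grade equals the screening grade. Illustrative cases:

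| Screening | Week 6 | True Week 16 | Recorded Week 16 | Result under 12.3.1 |
|---|---|---|---|---|
| 0 | 0 | 2 | 0 | real event missed |
| 1 | 1 | 2 | 1 | real event missed |
| 1 | 0 | 0 | 1 | false event, as an increase from the non-gradable Week 6 value |
| 1 | 0 | 2 | 1 | event flagged, grade too low |

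The comparison with baseline always shows no change. The comparison with a non-gradable Week 6 value can still show an increase, so the error can run in either direction.

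**How many participants.** Section 13.6 assumes remission of 45% on 1FED and 70% on 6FED, with 68 per group. Expected non-responders are 68 x 0.55 = 37.4 and 68 x 0.30 = 20.4, or 57.8 in total. About 58 is therefore a ceiling on Phase 2 entry at those rates, because Phase 2 is optional. The share with a clinical CBC in screening is not given. As a pure assumption, 10% to 50% of that ceiling would be 5.8 to 28.9, or about 6 to 29 participants.

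**The case against.** The best defence is that 9.7 contains a drafting slip that sites would see through. The item begins by telling staff to obtain a CBC and gives a blood volume. It never says that the clinical result replaces the draw. The Schedule marks the Visit 10 CBC without qualification. That stands as far as conduct goes: the documents do not show that any site entered a screening value at Week 16. It does not rescue the wording, because in 9.1 the same clause naturally works as a substitution.

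A reader might also infer four stronger things that the documents do not support.

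- *That an analysis of change in blood eosinophils or white cells is spoiled.* None is planned. CBC is not an endpoint in the protocol or a variable in the SAP; the SAP's eosinophil change is per high-power field in esophageal tissue. Section 12.1 does not name CBC among the safety assessments.
- *That the grade-increase definition can never be met after Phase 2.* Section 12.3.1 has a second comparator, as the third and fourth cases above show.
- *That monitoring for steroid toxicity is lost.* Section 12.2.1 lists immunosuppression as a potential risk, but section 6.1 calls it theoretical. The laboratory measure chosen in section 7.1.5 is morning cortisol, taken at the start and end of Phase 2 with no substitution clause.
- *That Week 6 has the same defect.* Section 9.4 has no screening-period wording and sits in a list of Week 6 procedures, to which the 3-day window applies. An explicit window there would only clarify.

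**Conclusion.** The point holds as a minor internal inconsistency: 9.7 is wrong as written and conflicts with the Schedule of Assessments. Read literally, it lets a count taken 17 to 28 weeks before a Week 16 visit, and before any study treatment, stand as the end-of-Phase-2 CBC. For the participants concerned, a laboratory adverse event at that visit could be missed, or a false one recorded if the Week 6 value was not gradable.

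This rests on two assumptions: that the clause works as a substitution, as it does in 9.1, and that the screening CBC is the baseline for grading. The number affected cannot be derived from the documents. The range of 6 to 29 depends on an assumed share and on full uptake of an optional phase, and the conclusion does not rely on it. The primary endpoint, the secondary and exploratory analyses and the cortisol monitoring are untouched.

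**What to change.** In section 9.7, replace the screening-period condition with the Week 16 visit window of plus or minus 3 days from section 9.9. A clinical CBC inside that window may be used; otherwise the CBC already marked at Visit 10 is obtained. Section 9.7 and the Schedule of Assessments then agree. Stating the matching Week 6 window in 9.4 is an optional clarification.

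For data already collected, compare the sample date of each Week 16 CBC with the visit date, and treat an entry carrying a screening date as missing at Week 16.

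The cost is a one-line amendment and a date check. No test is added, since the CBC is already scheduled, and no treatment or analysis changes.

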9.8 Unscheduled Visits

Unscheduled visits will take place for any complication or AE/SAE that requires an extra visit. The procedures to be performed at the unscheduled visits will be at the discretion of the PI. Procedures that may be performed at an unscheduled visit include:

- Vital signs (blood pressure, heart rate, respiratory rate, temperature), height and weight
- Physical exam
- Assess AEs

- Lab tests
- Assess/address problems with dietary adherence

These visits will be documented in the unscheduled visit case report.

9.9 Visit Windows

Study visits should take place within the time limits specified below: the designated visit windows (*i.e.* +/- *n* days) for each scheduled visit are also indicated on the Table 1 Schedule of Assessments.

Each visit window (for visits 2-10) is \pm 3 days.

10.MECHANISTIC ASSAYS

10.1 EDP

We will focus on molecular profiling of esophageal genes with the EoE Diagnostic Panel (EDP), a set of 94 mRNA transcripts that have been established to differentiate EoE from controls (e.g. GERD and normal individuals), and to identify exposure and transcriptional signaling to SGCs²⁸. The EDP is typically performed on an extra biopsy taken from the distal esophagus²⁸. If our hypotheses are proven to be correct, they have potential to transform monitoring of patients during therapeutic intervention, by identifying molecular markers that have therapeutic significance, and also by reducing the need for biopsies, particularly after therapy is initiated. Essentially, the associated EDP algorithm renders the raw Ct. values of each embedded gene after real-time PCR in a way such that the upregulated genes and downregulated genes are summed up individually. A quantitative “EoE score” is derived from the Δ Ct. (normalized to GAPDH) summation to reflect disease severity and for statistical analysis. Utilizing different gene sets, EDP is also able to predict steroid exposure and remission status based on the same algorithm²⁸. In this case, the EoE score will be calculated at baseline endoscopy and in the posttreatment biopsies to assess change with treatment.

